## 8.1.2 Laboratory test abnormalities

### 8.1.2.1 Definitions and reporting

Laboratory abnormalities will be assessed according to the Common Terminology Criteria for Adverse Events (CTCAE) version 4.03. Laboratory abnormalities that constitute an Adverse event in their own right (are considered clinically significant, induce clinical signs or symptoms, require concomitant therapy or require changes in study treatment), should be recorded on the Adverse Events eCRF. Whenever possible, a diagnosis, rather than a symptom should be provided (e.g. anemia instead of low hemoglobin). Laboratory abnormalities that meet the criteria for Adverse Events should be followed until they have returned to normal or an adequate explanation of the abnormality is found. When an abnormal laboratory or test result corresponds to a sign/symptom of an already reported adverse event, it is not necessary to separately record the lab/test result as an additional event.

Laboratory abnormalities, that do not meet the definition of an adverse event, should not be reported as adverse events. A Grade 3 or 4 event (severe) as per CTCAEv4.03 does not automatically indicate an SAE unless it meets the definition of serious as defined below and/or as per investigator's discretion. A dose hold or medication for the lab abnormality may be required by the protocol and is still, by definition, an adverse event.

## 8.2 Serious adverse events

### 8.2.1 Definitions

Serious adverse event (SAE) is defined as one of the following:

- Is fatal or life-threatening
- Results in persistent or significant disability/incapacity
- Constitutes a congenital anomaly/birth defect
- Is medically significant, i.e., defined as an event that jeopardizes the patient or may require medical or surgical intervention to prevent one of the outcomes listed above
- Requires inpatient hospitalization or prolongation of existing hospitalization,
- Note that hospitalizations for the following reasons should not be reported as serious adverse events:
  - Routine treatment or monitoring of the studied indication, not associated with any deterioration in condition (specify what this includes)
  - Elective or pre-planned treatment for a pre-existing condition that is unrelated to the indication under study and has not worsened since signing the informed consent
  - Treatment on an emergency outpatient basis for an event not fulfilling any of the definitions of a SAE given above and not resulting in hospital admission
  - Social reasons and respite care in the absence of any deterioration in the patient's general condition
- Note that treatment on an emergency outpatient basis that does not result in hospital admission and involves an event not fulfilling any of the definitions of a SAE given above is not a serious adverse event

### **8.2.2 Reporting**

To ensure patient safety, every SAE, **regardless of suspected causality**, occurring after the patient has provided informed consent and until at least 30 days after the patient has stopped study treatment must be reported to Novartis within 24 hours of learning of its occurrence.

SAE collection starts at time of ICF signature whether the patients is a screen failure or not.

Any SAEs experienced after this 30 days period should only be reported to Novartis if the investigator suspects a causal relationship to the study treatment. Recurrent episodes, complications, or progression of the initial SAE must be reported as follow-up to the original episode within 24 hours of the investigator receiving the follow-up information. An SAE occurring at a different time interval or otherwise considered completely unrelated to a previously reported one should be reported separately as a new event.

Information about all SAEs (either initial or follow up information) is collected and recorded on the Serious Adverse Event Report Form on a paper SAE Form. The investigator must assess and record the relationship of each SAE to each specific study treatment (if there is more than one study treatment), and complete the SAE Report Form in English.

The SAEs recorded on the paper SAE form should be faxed to [REDACTED] **within 24 hours of awareness of the SAE** to the local Novartis Chief Medical Office & Patient Safety (CMO&PS). The original copy of the SAE Report Form and the fax confirmation sheet must be kept with the case report form documentation at the study site.

Note that any follow up information provided should describe whether the event has resolved or continues, if and how it was treated, and whether the patient continued or withdrew from study participation. Each re-occurrence, complication, or progression of the original event should be reported as a follow-up to that event regardless of when it occurs.

Refer to [Section 7.1.1.2](#) for additional details regarding the reporting of SAEs which occur during the screening period.

### **8.3 Emergency unblinding of treatment assignment**

Not applicable

### **8.4 Pregnancies**

To ensure patient safety, each pregnancy occurring while the patient is on study treatment must be reported to Novartis within 24 hours of learning of its occurrence. The pregnancy should be followed up to determine outcome, including spontaneous or voluntary termination, details of the birth, and the presence or absence of any birth defects, congenital abnormalities, or maternal and/or newborn complications.

Pregnancy should be recorded on a Clinical Trial Pregnancy Form and reported by the investigator to the oncology Novartis CMO&PS department. Pregnancy follow-up should be recorded on the same form and should include an assessment of the possible relationship to the Novartis study treatment of any pregnancy outcome. Any SAE experienced during pregnancy must be reported on the SAE Report Form.

Pregnancy outcomes should be collected for the female partners of any males who took study treatment in this study. Consent to report information regarding these pregnancy outcomes should be obtained from the mother.

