- 29. Known diagnosis of human immunodeficiency virus (HIV) infection (HIV testing is not mandatory).
- 30. Patient has a history of non-compliance to medical regimen.
- 31. Pregnant or nursing (lactating) women, where pregnancy is defined as the state of a female after conception and until the termination of gestation, confirmed by a positive hCG laboratory test.
- 32. Women of child-bearing potential, defined as all women physiologically capable of becoming pregnant, unless they are using highly effective methods of contraception (defined below). Highly effective contraception must be used by both sexes (female patients and their male partners) during study treatment and for **8 weeks** after the last dose of study medication.

Highly effective contraception methods include:

- a. Total abstinence (when this is in line with the preferred and usual lifestyle of the subject). Periodic abstinence (e.g., calendar, ovulation, symptothermal, post-ovulation methods) and withdrawal are not acceptable methods of contraception
- b. Female sterilization (have had surgical bilateral oophorectomy with or without hysterectomy) or tubal ligation at least six weeks before taking study treatment. In case of oophorectomy alone, only when the reproductive status of the woman has been confirmed by follow up hormone level assessment
- c. Male partner sterilization (at least 6 months prior to screening). The vasectomized male partner should be the female study patient's sole partner
- d. Combination of the following (a+b or a+c, or b+c):
  - i. Use of oral, injected or implanted hormonal methods of contraception or other forms of hormonal contraception that have comparable efficacy (failure rate <1%), for example hormone vaginal ring or transdermal hormone contraception.
  - ii. Placement of a non-hormonal intrauterine device (IUD) or non-hormonal intrauterine system (IUS)
  - iii. Barrier methods of contraception: Condom or Occlusive cap (diaphragm or cervical/vault caps) with spermicidal foam/gel/film/cream/vaginal suppository

**Note :** In case of oral contraception, women should have been stable on the same pill for a minimum of 3 months before taking study treatment

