Women of child-bearing potential (sexually mature) who have not undergone a hysterectomy or who have not been naturally postmenopausal for at least 12 consecutive months (i.e., who has had menses any time in the preceding 12 consecutive months), must have a negative serum pregnancy test  $\leq$  14 days prior to starting study drug.

Post-menopausal women are allowed to participate in this study and do not require pregnancy or hCG laboratory test. Women are considered post-menopausal and not of child bearing potential if they have had 12 months of natural (spontaneous) amenorrhea with an appropriate clinical profile (e.g. age appropriate, history of vasomotor symptoms) or six months of spontaneous amenorrhea with serum FSH levels  $> 40$  mIU/mL or have had surgical bilateral oophorectomy (with or without hysterectomy) at least six weeks prior to entry in the study. In the case of oophorectomy alone, only when the reproductive status of the woman has been confirmed by follow up hormone level assessment, then she will be considered not of child bearing potential.

33. Fertile males must be willing to use contraception. Fertile males must use condom with spermicide (double barrier method). Highly effective contraception, as defined above, must be used by both sexes (male patients and their female partners) during study treatment and for 21 days after the last dose of study medication and should not father a child in this period. A condom is required to be used also by vasectomized men in order to prevent delivery of the drug via seminal fluid.

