#### 7.2.2.5.6 Pregnancy and assessments of fertility

Women of childbearing potential must undergo a serum pregnancy test at screening to confirm eligibility in the trial ( $\leq$  4 days before first dose of either study drug), and at EOT. Women of child-bearing potential must additionally undergo a monthly urine pregnancy test during the treatment phase.

In case of pregnancy, the patient must permanently stop study treatment immediately, withdraw from the trial, and the pregnancy must be reported on the Clinical Trial Pregnancy Form.

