### **11.3 Informed consent procedures**

Eligible patients may only be included in the study after providing written (witnessed, where required by law or regulation), IRB/IEC/REB-approved informed consent. Informed consent must be obtained before conducting any study-specific procedures (i.e. all of the procedures described in the protocol). The process of obtaining informed consent should be documented in the patient source documents. The date when a subject's Informed Consent was actually obtained will be captured in their eCRFs.

Novartis will provide investigators in a separate document with a proposed informed consent form (ICF) that is considered appropriate for this study and complies with the ICH and GCP guideline and regulatory requirements. Any changes to this ICF suggested by the investigator must be agreed to by Novartis before submission to the IRB/IEC/REB, and a copy of the approved version must be provided to the Novartis monitor after IRB/IEC approval.

Women of child bearing potential and fertile males should be informed that taking the study medication may involve unknown risks to the fetus if pregnancy were to occur during the study and agree that in order to participate in the study they must adhere to the contraception requirement for the duration of the study. Women of child bearing potential must agree to adhere to contraception requirement until at least 8 weeks after the final dose of study treatment. Fertile males must agree to adhere to contraception requirement until at least 21

days after the final dose of study treatment. If there is any question that the patient will not reliably comply, they should not be entered in the study.

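### Protocol section 8.4 makes pregnancy reporting in female patients mandatory only for pregnancies on study treatment, although contraception is required until 8 weeks after the last dose

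*Protocol*

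**What the plan says.** On reporting, protocol section 8.4 says that "each pregnancy occurring while the patient is on study treatment must be reported to Novartis within 24 hours". The next sentence asks for follow-up of outcome, including terminations, birth defects and maternal or newborn complications, for the pregnancy just described. For male patients the section is wider: "Pregnancy outcomes should be collected for the female partners of any males who took study treatment in this study", with no time limit.

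On contraception, exclusion criterion 32 in section 5.3 says "Highly effective contraception must be used by both sexes (female patients and their male partners) during study treatment and for", and the period it then gives is 8 weeks from the last dose. Section 11.3 repeats the period: "Women of child bearing potential must agree to adhere to contraception requirement until at least 8 weeks after the final dose of study treatment". The same paragraph tells patients that "taking the study medication may involve unknown risks to the fetus if pregnancy were to occur during the study". For male patients, exclusion criterion 33 applies "during study treatment and for 21 days after the last dose of study medication and should not father a child in this period".

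On testing, section 7.2.2.5.6 provides for serum tests at screening and at the end-of-treatment (EOT) visit, and says that "Women of child-bearing potential must additionally undergo a monthly urine pregnancy test during the treatment phase". No test is scheduled after EOT. The section also requires a pregnancy to be recorded on the pregnancy form, in the same sentence that tells the patient to stop treatment.

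**The concern.** The contraception rule for women runs 8 weeks beyond the last dose, while the duty to report and follow a pregnancy stops with treatment. The protocol asks women to avoid conceiving in those weeks on fetal-risk grounds. If one does conceive, a site that follows section 8.4 exactly has no duty to report the pregnancy or learn its outcome.

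What is at stake is the record of pregnancies close to exposure. Reporting from the time a pregnancy becomes known gives every outcome, normal births included, and so gives a denominator. Reporting only through serious adverse events (SAEs) gives a selected set. The male-partner clause, which is open-ended, makes the limit for female patients harder to explain, since they are the ones directly exposed. The documents give no reason for the difference.

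**Working it through.** The plan states no figure to reproduce. The check compares time windows, counted in days after the last dose unless noted.

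**Inputs for female patients**
- Contraception required: 8 weeks (sections 5.3 no. 32 and 11.3).
- Pregnancy reporting named after treatment: 0 days (section 8.4).
- Safety follow-up: 30 days, listing adverse events and concomitant medications, with pregnancy not named (section 7.1.4.1).
- SAE reporting: regardless of causality for 30 days, then only if the investigator suspects a causal link (section 8.2.2). A birth defect is an SAE; a pregnancy is not listed as one (section 8.2.1).
- Last scheduled pregnancy test: EOT visit, within 7 days of permanent discontinuation (section 7.1.3.1, Table 7-1).
- Survival contacts: every 3 months, survival status only (section 7.1.4.3).

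**Arithmetic**
- Contraception window: 8 × 7 = 56 days.
- Window with no stated duty to report a pregnancy as such: 56 − 0 = 56 days.
- Part also beyond the 30-day safety follow-up: 56 − 30 = 26 days.
- Part after the last test: this depends on how long after the last dose discontinuation is recorded, because EOT is timed from discontinuation. With EOT 7 days after discontinuation:
  - discontinuation on the day of the last dose: 56 − (0 + 7) = 49 days
  - discontinuation 7 days later, for example after an off week: 56 − (7 + 7) = 42 days
  - discontinuation 21 days later, after an interruption: 56 − (21 + 7) = 28 days

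These last three values are illustrations, not bounds.

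**Does another provision close the gap?**
- The reporting sentence in section 7.2.2.5.6 is framed for a patient who is still taking the drug. A positive EOT test could reasonably be handled under it, but a conception after EOT could not.
- Within 30 days an SAE is reportable whatever its cause, so a serious early complication would be seen. A pregnancy without an SAE would not.
- After day 30 an SAE is reportable only if causality is suspected. A birth defect after conception in the 8 weeks would come to light well after day 30, so it would depend on that judgment and on the site hearing of it.

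None of these requires the pregnancy itself to be reported and its outcome followed.

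**The case against.** Section 8.4 says what must be reported and does not forbid reporting more. Birth defects are SAEs, and section 8.4 adds that SAEs during pregnancy go on the SAE form, with no stated time limit. The documents nowhere say that the reporting period must equal the contraception period. The SAP plans no analysis of pregnancy incidence; its section 5.3 only lists pregnancy tests. Amendment 3 records that enrollment is closed and that one patient remained on study as of April 6, 2017, so the practical reach is small.

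Most of this stands, and it limits the point. Four stronger readings that a reader might infer are not supported:
- *Post-treatment pregnancies go unreported.* The text supports only that they need not be reported. Sites may report voluntarily, and the SAE routes remain. That the trial would go on to claim that no pregnancies occurred is speculation.
- *The 8 weeks are a declared exposure or fetal-risk window.* The protocol calls them a contraception requirement. Fetal risk is the reason given for it in section 11.3.
- *At least 49 of the 56 days are untested.* That assumes discontinuation coincides with the last dose, and the dosing break and permitted interruptions mean it may not.
- *Male partners are missed because the 21 days do not appear in section 8.4.* That clause has no time limit and already covers them.

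The objection does not remove the core mismatch. The SAE routes capture complications, some only after a causality judgment, and do not replace follow-up of the pregnancy.

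**Conclusion.** The mismatch is real and confined to female patients. For 56 days after the last dose the protocol requires contraception on fetal-risk grounds but does not require a pregnancy to be reported or followed as such; 26 of those days also lie beyond the 30-day safety follow-up. This is a modest weakness in safety capture that is cheap to correct. It does not affect the primary endpoint or any analysis in the SAP.

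The conclusion rests on reading section 8.4 as written and section 7.2.2.5.6 as addressed to a patient on treatment. The number of women of child-bearing potential is not given, so no expected count can be derived. Few events are likely in this advanced-cancer population, and the case rests on consistency and low cost, not on frequency.

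**What to change.** Reconcile section 8.4 with section 5.3 no. 32 and section 11.3:
1. Extend the reporting and follow-up duty for female patients to pregnancies on study treatment or within 8 weeks after the last dose. Write the duty into section 8.4 itself, because survival follow-up may be discontinued if the primary endpoint is not met (section 7.1.4.3).
2. Ask about pregnancy at the 30-day safety contact and, where it still takes place, at the first survival contact. The 30-day contact alone leaves the last 26 days unasked; the 3-month contact falls after the 8 weeks have ended.
3. Leave the male-partner clause unchanged. Adding a 21-day limit would narrow what is collected.

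This adds no test or visit and alters no contraception rule. The cost is an approved amendment (section 12.1), one sentence, one question and a small amount of data capture. Patients who transfer to the rollover study have no further safety or survival follow-up here (section 7.1.3.2), so these contacts would not reach them.

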## **8.5 Warnings and precautions**

No evidence available at the time of the approval of this study protocol indicated that special warnings or precautions were appropriate, other than those noted in the provided [Investigator's Brochure]. Additional safety information collected between IB updates will be communicated in the form of Investigator Notifications. This information will be included in the patient informed consent and should be discussed with the patient during the study as needed.

## **8.6 Data Monitoring Committee**

Not applicable

## **8.7 Steering Committee**

Not applicable

# **9 Data collection and management**

## **9.1 Data confidentiality**

Information about study subjects will be kept confidential and managed under the applicable laws and regulations. Those regulations require a signed subject authorization informing the subject of the following:

- What protected health information (PHI) will be collected from subjects in this study
- Who will have access to that information and why
- Who will use or disclose that information
- The rights of a research subject to revoke their authorization for use of their PHI.

In the event that a subject revokes authorization to collect or use PHI, the investigator, by regulation, retains the ability to use all information collected prior to the revocation of subject authorization. For subjects that have revoked authorization to collect or use PHI, attempts should be made to obtain permission to collect at least vital status (i.e. that the subject is alive) at the end of their scheduled study period.

The data collection system for this study uses built-in security features to encrypt all data for transmission in both directions, preventing unauthorized access to confidential participant information. Access to the system will be controlled by a sequence of individually assigned user identification codes and passwords, made available only to authorized personnel who have completed prerequisite training.

## 9.2 Site monitoring

Before study initiation, Novartis personnel (or designated CRO) will review the protocol and eCRFs with the investigators and their staff. During the study, the Investigator or designee will enter all required patient data into the eCRF within 72 hours (3 days) of the patient visit. The field monitor will visit the site regularly to check the completeness of patient records, the accuracy of entries on the eCRFs, the adherence to the protocol to Good Clinical Practice, the progress of enrollment, and to ensure that study treatment is being stored, dispensed, and accounted for according to specifications. Key study personnel must be available to assist the field monitor during these visits.

The investigator must maintain source documents for each patient in the study, consisting of case and visit notes (hospital or clinic medical records) containing demographic and medical information, laboratory data, electrocardiograms, and the results of any other tests or assessments. All information recorded on eCRFs must be traceable to source documents in the patient's file. The investigator must also keep the original signed informed consent form (a signed copy is given to the patient).

The investigator must give the monitor access to all relevant source documents to confirm their consistency with the eCRF entries. Novartis monitoring standards require full verification for the presence of informed consent, adherence to the inclusion/exclusion criteria and documentation of SAEs. Additional checks of the consistency of the source data with the eCRFs are performed according to the study-specific monitoring plan.

